## **6.2 Primary Study Endpoints**

- Safety profile: No adverse events greater than Grade 3-4
- Safety: Treatment-emergent adverse events (AEs)

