### 3.5.2 Dose Modifications

Dose of TFP will be discontinued in case of sustained increase of hemoglobin  $\geq 2$  gm/dL from the previous dose except those attributed to RBC transfusions. Dose should be held in the event of an AE  $\geq$  Grade 3 until resolution (to baseline) or  $\leq$  Grade 1. If AE is not resolved in 7 days then TFP will be discontinued. The guidelines for dose modifications are listed below.

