## 6 Study Design

### 6.1 General Design

This study is a multi-center, Phase I/II, dose escalation, open-label study to determine the safety of TFP in adult subjects with DBA and RBC-transfusion-dependence. A 3+3 dose escalation regimen will be used. The maximum time on study drug will be 21 days with a 1 week post-treatment follow-up period. It is expected that up to 24 subjects can be recruited and complete the study within 12-18 months. The dose escalation study design is shown in Figure 1:

- If 2 or more of the 6 subjects in Cohort B demonstrate toxicity  $\geq$  Grade 3, the study will be stopped, and 1 mg/day will be declared the MTD.
  - If  $< 2$  of the 6 subjects in Cohort B demonstrate toxicity  $\geq$  Grade 3 within 21 days of starting therapy, Cohort C will start.
3. Cohort C: Three subjects will receive TFP 5 mg PO daily.
- If there is no toxicity  $\geq$  Grade 3 at the end of the 21 days, Cohort D will start.
  - If 1/3 subjects in Cohort C demonstrates toxicity  $\geq$  Grade 3, an additional 3 subjects will be enrolled in Cohort C:
    - If 2 or more of the 6 subjects in Cohort C demonstrate toxicity  $\geq$  Grade 3, the study will be stopped, and 2 mg/day will be declared the MTD.
    - If  $< 2$  of the 6 subjects in Cohort C demonstrate toxicity  $\geq$  Grade 3 within 21 days of starting therapy, cohort D will start.
4. Cohort D: Three subjects will receive TFP 10 mg PO daily.
- If 0/3 subjects in Cohort D demonstrates toxicity  $\geq$  Grade 3, the study will be stopped, and 10 mg/day will be declared the MTD.
  - If 1/3 subjects in Cohort D demonstrates toxicity  $\geq$  Grade 3, an additional 3 subjects will be enrolled in Cohort D.
  - If 2 or more of the 6 subjects in Cohort D demonstrate toxicity  $\geq$  Grade 3, the study will be stopped, and 5 mg/day will be declared the MTD.
  - If  $< 2$  of the 6 subjects in Cohort D demonstrate toxicity  $\geq$  Grade 3 within 21 days of starting therapy, 10mg/day will be declared the MTD.

Each subject will undergo safety assessments as per the required schedule while on the study drug. All dosed subjects will be followed for an additional 1 week after discontinuing study drug (post-study safety follow-up). There will be no more than 6 subjects enrolled at any particular time.

Treatment will be discontinued for any subject if their Hb is > 12 gm/dL, not associated with RBC transfusions.

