**Primary Endpoint(s)**

- All AEs (including non-serious and serious) will be summarized. Key laboratory results will be summarized using CTCAE grade.

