## **15.2 Recording of Adverse Events (Appendix H)**

At each contact with the subject, the investigator must seek information on adverse events by specific questioning and, as appropriate, by examination. Toxicity will be scored using the NCI CTCAE, Version 5.0. A copy of the CTCAE, Version 5.0, can be downloaded from [https://ctep.cancer.gov/protocolDevelopment/electronic\\_applications/ctc.htm#ctc\\_50](https://ctep.cancer.gov/protocolDevelopment/electronic_applications/ctc.htm#ctc_50). All appropriate treatment areas should have access to a copy of the CTCAE, Version 5.0. All adverse clinical experiences, whether observed by the investigator or reported by the subject, must be recorded, with details about the duration and intensity of each episode, the action taken with respect to the test drug, and the subject's outcome. The investigator must evaluate each adverse experience for its relationship to the test drug and for its seriousness.

The study sponsor shall notify the FDA by telephone or by facsimile transmission of any unexpected fatal or life-threatening experience associated with the use of the drug as soon as possible but no later than 7 calendar days from the sponsor's original receipt of the information.

All other SAEs that meet the criteria for reporting to the FDA must be reported to the FDA within 15 calendar days after awareness of the event. A clear description of the suspected reaction should be provided along with an assessment as to whether the event is drug or disease related.

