## **15.4 Stopping Rules**

The stopping rules are as follows:

Scenario 1: The occurrence of extrapyramidal symptoms, symptoms suggestive of tardive dyskinesia (including vermicular movements of the tongue), neuroleptic malignant syndrome or any SAE or treatment-emergent AE  $\geq$  Grade 3 felt to be causally related to TFP in a single subject:

- Rule: Treatment will be immediately stopped in that subject and the subject will be discontinued from the study.

Scenario 2: The occurrence of the extrapyramidal symptoms, symptoms suggestive of tardive dyskinesia (including vermicular movements of the tongue), neuroleptic malignant syndrome or the same SAE or treatment-emergent AE  $\geq$  Grade 3 felt to be causally related to TFP in more than 1 subject:

- Rules:
  - a. Treatment will be immediately stopped in those subjects and those subjects will be discontinued from the study.
  - b. If the 2 or more subjects are in Cohort A, the trial will be stopped; no MTD will be declared.
  - c. If the 2 or more subjects are in Cohort B, the study will be stopped, and 1 mg/day will be declared the MTD.

- d. If the 2 or more subjects are in Cohort C, the study will be stopped, and 2 mg/day will be declared the MTD.
- e. If the 2 or more subjects are in Cohort D, the study will be stopped, and 5 mg/day will be declared the MTD.

Scenario 3: Hemoglobin > 12 mg/dL in a subject sustained for more than 7 days (not associated with RBC transfusion)

- Rule: The subject will be considered a complete responder, treatment will be discontinued, and the duration of the effect will be monitored until day 29 after start of treatment.

In addition to the stopping rules, a subject may be discontinued by the investigator at any time for failure to comply with protocol requirements, in the event that the investigator feels that continuation in the study poses a risk to the health of the subject, or if the subject withdraws consent.

The reason for treatment discontinuation must be documented in the subject chart / source records.

The trial will be stopped, as noted above, if more than one subject experiences the occurrence of the extrapyramidal symptoms, symptoms suggestive of tardive dyskinesia, neuroleptic malignant syndrome, the same SAE or treatment-emergent AE  $\geq$  Grade 3 felt to be causally related to TFP at the lowest dose level.

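### The first primary endpoint in 6.2 is ambiguous, and on either reading of its comparator it is laxer than the Grade 3 or higher threshold that drives escalation in 6.1

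*Combined protocol and SAP*

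**What the plan says.** The only graded statement of a primary endpoint is the first bullet of 6.2: "No adverse events greater than Grade 3-4". The second bullet lists treatment-emergent adverse events with no grade attached. Section 6.4 describes the primary safety endpoint only as evaluating the safety profile, so it does not settle the threshold.

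On grading, 15.2 states: "Toxicity will be scored using the NCI CTCAE, Version 5.0". Appendix H cites the same scale. Neither prints it.

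Elsewhere the line is Grade 3 or higher:

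- **Escalation and MTD (6.1).** The cohort rules, such as those beginning "If 0/3 subjects in Cohort D demonstrates toxicity" and "If 2 or more of the 6 subjects in Cohort C demonstrate toxicity", go on to name Grade 3 or higher. Two or more of six subjects stops the study, and the next lower dose is declared the MTD. Several of these rules state a 21-day window.
- **Dose hold (3.5.2).** The rule beginning "Dose should be held in the event of an AE" is set at Grade 3 or higher.
- **Withdrawal (7.6.1)** and **re-entry to a later cohort (7.2, criterion 6)** use the same grade.
- **Stopping (15.4).** The same grade applies, with a causal relation to the drug required. It also covers serious adverse events and named neurological events. For the lowest dose: "If the 2 or more subjects are in Cohort A, the trial will be stopped; no MTD will be declared".

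The primary analysis in 14.2 is descriptive: "All AEs (including non-serious and serious) will be summarized". Key laboratory results are summarised by CTCAE grade. The section neither restates nor clarifies the 6.2 threshold.

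**The concern.** Safety is the trial's only stated objective in section 4, and this bullet heads its list of primary endpoints. A threshold that admits more than one reading is not prespecified. In an open-label study, the reading could be chosen after the data are known.

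The larger difficulty is that both readings of the comparator sit above the line the trial acts on. The same cohort could be rejected under 6.1 and show no failures on the first primary endpoint. The results are meant to support a proof-of-concept trial or a modified compound (section 2), so the endpoint and the escalation outcome should not point in different directions.

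**Working it through.** **The plan's own figure.** Section 14.1 gives 3 to 24 subjects for four 3+3 cohorts. Minimum: 1 cohort × 3 = 3. Maximum: 4 cohorts × 6 = 24. Both reproduce. The plan states no alpha, power or effect size to check.

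**Step 1: which events count.** Inputs are the 6.2 wording, the 6.1 threshold, and an assumed five-grade scale with 5 the highest. Each subject is classified by worst grade.

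| Worst grade | 6.2 read as above 4 | 6.2 read as above 3 | 6.1 (3 or higher) |
|---|---|---|---|
| 1 or 2 | not counted | not counted | not counted |
| 3 | not counted | not counted | counted |
| 4 | not counted | counted | counted |
| 5 | counted | counted | counted |

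The Grade 3 row is the same on both readings of 6.2 and differs from 6.1. Only the Grade 4 row depends on which reading is taken.

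**Step 2: one cohort.** Suppose 2 of 6 subjects in Cohort D have Grade 3 toxicity within 21 days and nobody has anything worse.

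- Under 6.1: 2/6 = 33%. The study stops and 5 mg/day is declared the MTD.
- Under the 6.2 bullet, either reading: 0/6 = 0%.

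If those two events were Grade 4, the bullet gives 0/6 when read as above 4 and 2/6 when read as above 3.

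**Step 3: how often 6.1 rejects a cohort.** Let p be the true probability of Grade 3 or higher toxicity per subject. The plan gives no value, so these are illustrative. I take two or more toxicities among the first three as stopping too. Then

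P(reject) = 1 − [(1 − p)³ + 3p(1 − p)² × (1 − p)³].

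- p = 0.10: 1 − (0.729 + 0.243 × 0.729) = 0.094
- p = 0.20: 1 − (0.512 + 0.384 × 0.512) = 0.291
- p = 0.50: 1 − (0.125 + 0.375 × 0.125) = 0.828

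These are upper bounds on the chance that a cohort is rejected while the bullet shows no failures. The bound is reached only if every toxicity falls below the bullet's line: all Grade 3 if it means above 3, all Grade 3 or 4 if it means above 4.

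**The case against.** The strongest reply is that this is a drafting slip with no operational effect, and much of that stands. The authors probably meant no Grade 3-4 events, or none of Grade 3 or higher. No escalation, hold, withdrawal or stopping decision uses the bullet. The second bullet of 6.2 covers all treatment-emergent events, 14.2 summarises all adverse events, and 15.6 tabulates each type as a percentage of subjects. The MTD is itself a stated result (Study Summary), so a dose rejected for toxicity would be visible as such. The plan also contains no formal met or not-met test on this bullet: 14.2 is descriptive, and the Study Summary gives the statistical methodology as not applicable.

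A reader might go further and infer any of the following. The documents do not support them.

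- **That the endpoint certainly fails only on the top grade, so every subject could have Grade 3 or 4 toxicity and it would still be met.** This takes one reading as fact and assumes a scale the protocol cites but does not print. If the bullet means above Grade 3, Grade 4 events count.
- **That Grade 3-4 events would go unreported or unacted on.** The independent rules and the summaries above rule this out.
- **That all 24 subjects could have such toxicity with the endpoint intact.** Universal Grade 3 or higher toxicity in an early cohort would stop the trial before later cohorts opened.
- **That 14.2 analyses nothing in 6.2.** It covers the second bullet directly; only the graded criterion is missing.

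What survives the reply is narrow. The intended threshold is not what the text says, both readings of its comparator disagree with 6.1, and no other section corrects it.

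**Conclusion.** The bullet is wrong as written and should be corrected, but it is not a defect that must hold up the trial. It is ambiguous between above Grade 3 and above Grade 4, and on both readings it is laxer than the threshold the protocol uses everywhere else. In the worked cohort the discrepancy is 0/6 against 2/6 (33%). That result needs only the 6.1 threshold and the words of 6.2, with failures counted per subject, a unit 6.2 does not state. Extending it to Grade 4 events needs two further assumptions: the above-4 reading and a five-grade scale. The effect is confined to the definition and reporting of the primary endpoint.

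**What to change.** Reconcile 6.2 with 6.1 in three small edits.

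1. Restate the first bullet of 6.2 as the number and proportion of dosed subjects at each dose level with toxicity as counted by the 6.1 rules: same grade threshold, same event definition, same 21-day window. Refer to 6.1 rather than writing a second definition, so that the two cannot drift apart.
2. List that proportion in the 14.2 primary analysis, using the population of subjects with at least one dose already defined there. An exact confidence interval is optional; for 2/6 the 95% interval is about 4% to 78%.
3. Report Grade 3 or higher adverse events through the 7-day follow-up separately.

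The third edit is needed because matching on grade alone is not enough. Adverse events are recorded until 7 days after the last dose (15.1), whereas 6.1 speaks of toxicity and, in several rules, of 21 days. An endpoint counting every treatment-emergent event of Grade 3 or higher through follow-up could still disagree with the escalation outcome, for example on a late event.

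The cost is about two sentences for the endpoint and its analysis, plus one reporting line. No new data, visits or subjects are needed, and the range of 3 to 24 is unchanged. The downside is that the reported endpoint becomes less favourable.

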## **6.3 Secondary Study Endpoints**

- Pharmacodynamic markers of TFP target engagement

## **6.4 Primary Safety Endpoints**

The primary safety endpoint is to evaluate the safety profile of TFP for red blood cell transfusion-dependent adults with DBA.

## **7 Subject Selection and Withdrawal**

### **7.1 *Inclusion Criteria***

In order to be eligible to participate subjects must meet all of the following criteria:

1. Men and women age:  $\geq 18$  years and  $< 65$  years of age.
2. Weight:  $\geq 45$  kilograms.
3. DBA diagnosed according to the DBA criteria (Vlachos, 2008) (Appendix B).
4. RBC transfusion-dependence (defined as 2 units packed RBCs per 28 days averaged over 84 days [12 weeks] prior to study entry) (Gale, 2011) (Appendix C).
5. Calculated creatinine clearance  $\geq 30$  mL/min (Appendix D).
6. Karnofsky performance status scale score  $\geq 70$  (Appendix E).
7. Female subjects of childbearing potential participating in the study are to use highly effective methods of birth control (abstinence, oral contraceptives, barrier method with spermicide or surgical sterilization) during study participation and for 1 week following the last dose of TFP (a total of 4 weeks of the study). Female subjects of childbearing potential must have a negative serum  $\beta$ -human chorionic gonadotropin pregnancy test within 3 days prior to the start of TFP given on Day 1. Subjects must be counseled concerning measures to be used to prevent pregnancy and potential toxicities prior to the first dose of TFP. A female subject of childbearing potential is a sexually mature woman who has not undergone a hysterectomy or bilateral oophorectomy; or who has not been postmenopausal for at least 24 consecutive months (i.e., who has had menses at some time in the preceding 24 months).
8. Male subjects must agree to use a latex condom during any sexual contact with females of childbearing potential while participating in the study and for 1 week following the last dose of TFP, even if he has undergone a successful vasectomy (a total of 4 weeks of the study). Male subjects must be counseled concerning measures to be used to prevent pregnancy and potential toxicities prior to the first dose of TFP.
9. Agreement to adhere to the study visit schedule, understand and comply with all protocol requirements.
10. The subjects are capable of giving informed consent.

## 7.2 Exclusion Criteria

Subjects who meet any of the following criteria will not be eligible to participate in the study:

1. Liver: aspartate aminotransferase (AST) > 5 x the upper limit of normal (ULN), alanine aminotransferase (ALT) >5 x ULN, or bilirubin > 5 x ULN.
2. Heart disease (New York Heart Association classification of  $\geq 3$ ; Appendix F).
3. History of angina.
4. Uncontrolled hypertension. If hypertension is considered clinically stable, systolic blood pressure must be <150 mmHg or diastolic blood pressure must be <100 mmHg.
5. Subjects currently responsive to corticosteroids for treatment of DBA.
6. Treatment with another investigational drug or device <56 days pre-study entry. Subjects who participated in an earlier cohort of this trial may participate in a subsequent cohort if (a) they meet all eligibility criteria, (b) did not experience any adverse effects  $\geq$  Grade 3 while on TFP, and (c) discontinued TFP  $\geq$  6 days (10 half-lives) prior to day 1 of the subsequent cohort.
7. Pregnant or lactating females.
8. Any history of severe allergic reaction requiring the use of epinephrine.
9. Known hypersensitivity to the study drug or other phenothiazines.
10. History or presence of extrapyramidal signs.
11. History of cancer.

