### **9.1 Screening**

The Screening Period is from Day -28 to Day -1 prior to the subject starting the study drug on Day 1 of the study. If consent was not previously obtained by mail then the PI will obtain informed consent at a Screening visit. If the consent was obtained by mail then the consent will be reviewed again with the subject at the initial visit. The subject will be then be assessed for inclusion and exclusion criteria with a review of his/her medical record, including prior treatments, procedures, and transfusion history (for the previous 12 weeks at least). A physical examination including height at 1st visit, weight, vital signs, blood pressure and neurological exam will be performed on the subject. Karnofsky performance status will be assessed. Blood work will be performed for a complete blood count (CBC; RBC count, hemoglobin, hematocrit, absolute reticulocyte count, white blood cell count, absolute neutrophil count, and

platelet count), serum chemistry panel for hepatic and renal function (blood urea nitrogen, creatinine, bilirubin [total and direct], aspartate aminotransferase [AST], and alanine aminotransferase [ALT]). If the subject is a female, then menstrual status will be assessed and a serum pregnancy test will also be performed. If all the criteria are evaluated and subject is confirmed to start the study, Screening and Visit 1 may be combined into one visit and the Screening blood work can be used as the Visit 1 blood work if within  $\pm$  1 day.

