## **14 Statistical Plan**

### **14.1 *Sample Size Determination***

This is a 4-Cohort, 3+3 study, and will therefore enroll a minimum of 3 patients and a maximum of 24 patients. Sample size power to detect a given effect does not apply.

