#### **Exclusion Criteria**

- Have a known allergy to TFP or other phenothiazines (class of drugs including TFP)
- Evidence of kidney or liver dysfunction
- Evidence of heart disease or history of angina
- Uncontrolled high blood pressure
- Pregnancy, or plans to become pregnant during duration of trial
- History of cancer

Please refer to the website link: <http://www.clinicaltrials.gov> and enter the search term “Diamond-Blackfan Anemia and trifluoperazine” for full eligibility criteria and additional trial information.

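### The blood-pressure check in exclusion 4 joins its two limits with *or*, so a subject judged stable passes it with one pressure far above its limit

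*Combined protocol and SAP*

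**What the plan says.** Section 7.2 opens its list with the rule that "Subjects who meet any of the following criteria will not be eligible to participate in the study". Item 4 then has two parts. It names a condition and introduces a qualification: "Uncontrolled hypertension. If hypertension is considered clinically stable". The qualification is that "systolic blood pressure must be <150 mmHg or diastolic blood pressure must be <100 mmHg".

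No other section gives a blood-pressure limit. The study announcement in Appendix G (Section 22.7) repeats only the general exclusion, "Uncontrolled high blood pressure", with no figures. Section 9.1 provides for the measurement at screening ("weight, vital signs, blood pressure and neurological exam will be performed on the subject") but sets no threshold. Sections 7.4 and 9.2 and the schedule in Appendix A also list blood pressure without a limit. The terms *uncontrolled* and *clinically stable* are not defined anywhere in the documents.

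**The concern.** The numeric sentence is there to put an objective bound on which subjects with treated or known hypertension may enter. Joined by *or*, the two limits do not bound either pressure: once one is met, the other has no ceiling. That sits badly with an item whose stated purpose is to keep out uncontrolled hypertension.

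What is at stake is whether eligibility is applied uniformly and can be verified. Section 6.1 calls the study multi-center, and the Study Summary allows further centers if enrollment is slow. One investigator may follow the sentence literally. Another may read it as if both limits had to hold. Both could defend their reading, and a monitor checking source data would have no firm rule to check against.

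**Working it through.** No sample-size or error-rate figure bears on this. Section 14.1 says "Sample size power to detect a given effect does not apply", so there is no planned figure to reproduce. The check is one of logic.

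**Inputs.** From Section 7.2, item 4: systolic limit 150 mmHg, diastolic limit 100 mmHg, connector *or*, both stated as values the subject must be below. Let S be systolic and D diastolic pressure in mmHg.

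**As written.** Pass if S < 150 or D < 100. Negating this, fail only if S ≥ 150 and D ≥ 100.

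**With both limits required.** Pass if S < 150 and D < 100. Fail if S ≥ 150 or D ≥ 100.

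The pairs below are assumed for illustration. Each is taken to belong to a subject already judged clinically stable.

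| Reading (S/D) | S < 150 | D < 100 | As written (*or*) | Both required (*and*) |
|---|---|---|---|---|
| 140/90 | yes | yes | pass | pass |
| 149/99 | yes | yes | pass | pass |
| 150/99 | no | yes | pass | fail |
| 149/100 | yes | no | pass | fail |
| 190/95 | no | yes | pass | fail |
| 145/115 | yes | no | pass | fail |
| 220/99 | no | yes | pass | fail |
| 150/100 | no | no | fail | fail |
| 190/120 | no | no | fail | fail |

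The two versions differ exactly where one limit is breached alone. At 220/99 the systolic value is 220 − 150 = 70 mmHg above its limit and the check is still passed.

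**Comparison within the same list.** Item 1 of Section 7.2 also uses *or*, between AST, ALT and bilirubin each above 5 times the upper limit of normal. There each limb is a reason to exclude, so *or* is the strict connector: any one breach excludes. Item 4 turns its limits round into conditions to be met but keeps the same connector, which makes it the permissive one. This suggests a drafting slip, though the documents do not confirm it.

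**The case against.** The strongest reply is that nobody with uncontrolled hypertension is let in. The first sentence of item 4 excludes them outright, and Appendix G repeats that exclusion without qualification. The limits come afterwards, as an added necessary condition for subjects already judged stable; they are not sufficient for entry. An investigator who sees 190/95 can call it uncontrolled and stop there. This stands, and it sets the size of the point. A reader might infer that such a subject qualifies or is admitted as written; the text supports only that the subject passes the numeric part if judged stable. Nor do the documents say that the two limits define acceptable control.

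The reply does not remove the defect. The judgement it relies on is undefined, and the numeric sentence applies precisely to subjects about whom that judgement has already been made favourably. It is the only objective constraint on the judgement, and it is weak.

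Two further inferences are tempting and should not be drawn.

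- **Harm from the drug.** Section 10 lists hypotension and cardiac arrest among phenothiazine reactions, but nothing in the documents links high baseline pressure to trifluoperazine toxicity. The other cardiac exclusions in Section 7.2 (New York Heart Association class 3 or above, history of angina) still apply.
- **Distortion of dose escalation.** A reader might argue that unrelated cardiovascular events would enter cohorts of three, where one subject is a third of the data. That fraction holds for any subject with any trait. Under Section 15.1 a pre-existing condition becomes an adverse event only if it worsens, and the stopping rules in Section 15.4 require events of Grade 3 or above to be judged related to the drug. Section 6.1 counts toxicity without stating attribution, but that is a separate question and does not follow from this connector.

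**Conclusion.** The point holds as a defect in a stated eligibility rule. Read literally, the check in exclusion 4 fails only when both limits are reached or exceeded, so a subject judged clinically stable passes it with one pressure far above its limit. What is left is a numeric check that adds little to an undefined judgement and does not serve the exclusion it belongs to.

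The conclusion rests on the literal meaning of the sentence and on there being no other limit or definition in the documents. It does not rest on the example readings. Its practical size is unknown: the documents give no frequency of hypertension in this population or of readings that breach one limit alone, and the number of subjects affected may be small. The endpoints, the analysis and the planned 3 to 24 subjects are not touched.

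**What to change.** Reconcile the two parts of item 4. The simplest change is to replace *or* with *and* in the numeric sentence, so that both existing limits must be met, with the limits themselves unchanged. If the sponsor really means that one limit is enough, the item should say so in terms and explain how that fits with excluding uncontrolled hypertension.

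The change is one word. It needs no new procedure, since pressure is already measured at screening. Some candidates above a single limit could become ineligible; the documents give no basis for saying how many.

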#### **3.5.1 Dose Escalation**

Up to 4 cohort dose levels of TFP will be studied: 1, 2, 5, and 10 mg/day for up to 21 days each, as tolerated. Cohort A will start at 1 mg/day, and the dose will escalate to 2 mg/day in Cohort B, 5 mg/day in Cohort C, and 10 mg/day in Cohort D. At the start of each cohort, 3 subjects will be enrolled, and an interim analysis (IA) for safety and tolerability will be

conducted after all 3 subjects have completed 21 days of treatment (See [Section 6 Study Design](#) for details). The 21-day time frame is based on the t1/2 from the healthy volunteer 5 mg single dose TFP study ([Midha, 1983](#)), showing that TFP's elimination t1/2 is approximately 12-14 hours. Therefore, steady state is reached approximately 3 days after initiating therapy, and 21 days of therapy provides at least 18 days of exposure at steady state (the 1 and 2 mg doses likely have shorter t1/2 and so steady state will be reached even sooner in the first 2 cohorts).

Whereas some FIH trials may use an enrollment restriction rule such that only two subjects are dosed at a time, this trial will not use such an enrollment restriction design. Please see [Section 2 Brief Summary of Research](#) for the supporting rationale.

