## 5 Resources Available to Conduct the Human Research

[name] is the PI and sponsor of this study and the Director of the Diamond Blackfan Anemia Registry (DBAR) of North America. The DBAR is housed at the Feinstein Institute for Medical Research. There are over 750 subjects with Diamond Blackfan anemia enrolled in the DBAR. Because of this, the investigator has access to the specific subject population required for this study. Subjects/parents of subjects and their physicians contact the DBAR periodically to inquire about available studies. Also, the DBA Foundation (DBAF), the family support group, has access to most of the DBA families. The DBAF is highly supportive of the research and they also encourage the families to contact the DBAR for any available studies. We have prepared an announcement to inform the subjects of the study as we have for other studies in the past. This has worked well previously, and we do not expect having any issues in recruiting subjects.

With regards to the trial logistics, the protocol is reviewed at the site initiation visit with all study personnel, along with the trial-related duties and functions.

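### Re-entrants are pre-selected for tolerating a lower dose, and no readable text limits or separates them in the 3+3 count, so a declared MTD may not describe TFP-naive patients

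*Combined protocol and SAP*

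**What the plan says.** Section 6.1 states: "A 3+3 dose escalation regimen will be used". Section 3.5.1 adds: "At the start of each cohort, 3 subjects will be enrolled". If one of the three has a toxicity of Grade 3 or higher, the cohort expands (for 5 mg, "an additional 3 subjects will be enrolled in Cohort C"), and it clears with fewer than 2 of 6. At 10 mg, 0 of 3 is enough: "the study will be stopped, and 10 mg/day will be declared the MTD".

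Section 7.2, item 6, allows re-entry: "Subjects who participated in an earlier cohort of this trial may participate in a subsequent cohort if" three conditions hold. One is that they "did not experience any adverse effects" of Grade 3 or higher on TFP. Two other provisions filter in the same direction. Item 10 excludes anyone with a history of extrapyramidal signs, and Section 15.4, Scenario 1, takes subjects with extrapyramidal symptoms out of the study.

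The only enrolment cap in Section 6.1 is 6 subjects at one time. Section 8.3 enrols everyone who qualifies and gives TFP-naive subjects no priority. Sections 14.1 to 14.3 do not mention a person who appears in more than one cohort; Section 14.1 says only that the trial "will therefore enroll a minimum of 3 patients and a maximum of 24 patients". Section 8.9.3 says that a subject gets study drug a single time in the study, which, read literally, would rule out re-entry.

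The start of the Section 6.1 list (Cohort A and part of Cohort B) and Figure 1 are missing from the text available for this review, so the absence of a cap is established only for what can be read.

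**The concern.** A 3+3 count informs about a dose only if the 3 or 6 people are a fair sample of those who would receive it. Here re-entrants have been screened on the very event that the rule counts. Selection bites if tolerance at one dose predicts tolerance at the next. The protocol gives grounds to expect that: Section 3.5 calls side effects dose- or plasma-level-related, and Section 3.2.2 reports large differences between people after the same 5 mg dose (AUC 5.9 to 17.6, peak 0.53 to 3.09 ng/mL). Low-exposure people are likelier to pass the filter.

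At stake is what the declared MTD means. Section 2 presents the trial as support for a possible proof-of-concept study. An MTD reached on pre-selected subjects could look safer than it is for patients starting TFP at that dose.

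**Working it through.** **The plan's own figure.** 4 cohorts × (3 + 3) = 24, and the minimum is 3 if Cohort A ends the trial. Both figures in Section 14.1 reproduce, but as cohort slots. With re-entry, four cohorts at 0/3 (12 slots) could be filled by 3 people. Four expanded cohorts with one toxicity each (24 slots) could be filled by 6 + 1 + 1 + 1 = 9.

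**Washout.** Ten half-lives of 12 to 14 hours are 5.0 to 5.8 days, so 6 days deals with drug carry-over. It does nothing about selection.

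**Clearance rule.** A dose clears with 0/3, or with 1/3 and then no event in the next three. If every slot has rate p:

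P(clear) = (1−p)³ + 3p(1−p)² × (1−p)³

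- p = 0.33: 0.301 + 0.444 × 0.301 = 0.434
- p = 0.40: 0.216 + 0.432 × 0.216 = 0.309

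**How many re-entrants Cohort D can have from 5 mg.** Cohort D opens after 0/3 in Cohort C (three tolerators) or 1/6 (five). Six cannot arise.

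**Rate among re-entrants (assumption: fixed personal tolerance).** c = (p10 − p5)/(1 − p5). Re-entrants fill the first slots and TFP-naive subjects the rest:

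- three re-entrants: (1−c)³ + 3c(1−c)² × (1−p10)³
- five re-entrants: (1−c)³ + 3c(1−c)² × (1−c)²(1−p10)

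For 15%/33%, c = 0.18/0.85 = 0.212. Three give 0.490 + 0.395 × 0.301 = 0.609; five give 0.490 + 0.395 × 0.416 = 0.654.

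| Assumed rates, 5 mg / 10 mg | c | All naive | 3 re-entrants | 5 re-entrants |
|---|---|---|---|---|
| 20% / 40% | 0.250 | 31% | 51% | 56% |
| 15% / 33% | 0.212 | 43% | 61% | 65% |
| 5% / 33% | 0.295 | 43% | 48% | 50% |
| 2% / 33% | 0.316 | 43% | 45% | 46% |
| 0% / 33% | 0.330 | 43% | 43% | 43% |

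If the remaining slots went to people who had tolerated only 1 or 2 mg, the results would lie somewhat above these.

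**Weaker dependence.** With logit-normal susceptibility of SD 1, 2 and 3 and rates of 20%/40%, c = 0.364, 0.316 and 0.287. Clearance is 35%, 42% and 46% with three re-entrants, and 36%, 44% and 50% with five, against 31%.

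**Whole trial.** This was simulated (20,000 runs per scenario) with normally distributed latent tolerance, within-person correlation rho, and earlier tolerators filling slots first. At true rates of 5/10/20/40%, 10 mg is declared the MTD in about 19% of trials with fresh subjects. With full re-entry it is about 32% (rho = 0.5) or 41% (rho = 1), using about 5 distinct people on average instead of 13. At 2/5/10/40% the figures are 27%, 34% and 37%. With rho = 0 nothing material changes.

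**The case against.** The strongest reply is that the assumed rates are high for these doses. Sections 2 and 3.4 cite a trial in which 2–6 mg/day had a side-effect profile close to placebo, and a comparison in which 15 mg/day did not differ from placebo in severe adverse effects, Parkinsonism or dystonia. Those are other populations, but they are the only clinical evidence in the documents, and they point to the bottom rows of the table. This stands.

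The direction is not certain either. Re-entrants carry more cumulative exposure, up to 3 × 21 = 63 days before Cohort D. Section 2 links the expected neurologic toxicity to long-term use at antipsychotic doses. That could offset part of the selection, and the documents do not let one say how much.

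Re-entry is also a deliberate choice, with stated conditions, in a rare disease. Section 5 says "we do not expect having any issues in recruiting subjects", but the Study Summary allows for more centres should accrual lag. This is a reason not to forbid re-entry. It is not a reason to leave re-entrants unidentified in the count.

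A reader might infer a larger effect by giving all six Cohort D slots to 5 mg tolerators, which yields 68% for 15%/33% and 60% for 20%/40%. The escalation rule cannot produce six such people, so those figures are bounds that are never reached. Nor do the documents support saying that the MTD will be biased: that depends on how many re-entrants are used, on the lower-dose rate and on the correlation.

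**Conclusion.** The concern holds in conditional form. As written, the plan lets a dose be cleared, and declared the MTD, largely or wholly on people selected for tolerating a lower dose, and the planned summaries would not show it. For one step from 5 to 10 mg under fixed tolerance, the gain in the chance of clearing is about 18 to 25 points when the 5 mg rate is 15–20%, about 5 to 6 points at 5%, about 2 at 2%, and none at zero or without correlation across doses. The documents' own safety evidence favours the low end. No stated figure is wrong, but 3 and 24 are ambiguous between people and slots.

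**What to change.** 1. In Sections 6.1 and 14.2: for each dose decision and for the declared MTD, report the Grade 3 or higher count among first-course subjects (x/n) beside the total, and the number of distinct people.
2. State that a dose cleared with re-entrants was shown tolerable in subjects pre-selected on a lower dose, not in TFP-naive subjects.
3. In Section 14.1, say whether 3 to 24 counts people or cohort slots.
4. Reconcile Section 7.2, item 6, with the single-receipt sentence in Section 8.9.3. That sentence probably means one dispensing per course, but it should say so.

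The cost is an extra column or two in the safety table and a few sentences. Accrual and the escalation rule are untouched.

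A stricter remedy would let only first-course subjects count toward clearing a dose, while toxicities in re-entrants still count against it. That rewrites the escalation rule, leaves the denominator undefined (0/3 first-course plus one re-entrant toxicity has no assigned action), pushes clearance below the usual 3+3 value and may slow accrual. Whether re-entrants may fill decision slots is for the sponsor to decide and state.
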